8.10 Safety Endpoint Analyses

The safety evaluation will be purely descriptive using descriptive statistics (N, mean, SD, median minimum and maximum) or frequency tables where appropriate using the MITT analysis set, unless otherwise specified. No imputation will be made in case of missing values.

8.10.1 Adverse Events

Adverse events (AEs) will be coded using MedDRA dictionary. If an incomplete or missing onset date was collected for an AE, the imputation method of missing data specified in Section 8.1.5 will be applied. Treatment-emergent AEs (TEAEs) are defined as AEs that started or worsened in severity on or after the SFISD. The relationship to study treatment for each AE will be classified as 'Unrelated', 'Unlikely Related', 'Possibly Related', 'Probable Related', 'Definite Related'. AEs classified as 'Possibly Related', 'Probable Related', or 'Definite Related' will be analyzed as 'Related' in the AE summaries. Data listings, patient narratives, etc. will present the relationship to study treatment as collected on the eCRF.

8.10.1.1 Tabulations of TEAEs

The frequency and incidence of TEAEs will be summarized by System Organ Class (SOC) and Preferred Term (PT) by treatment and then by overall treatment. The actual version of the MedDRA coding dictionary used will be noted in the clinical study report. The SOC is sorted by alphabetic order; then within SOC, PT is sorted by descending counts under Auxora Total column, then descending counts under placebo column, then alphabetic order for PTs with the same count.

Each of the summaries will be done at the subject level. Multiple occurrences of the same event within a subject will be counted once in the summaries by SOC and PT.

All AEs for each subject, including multiple occurrences of the same event, will be presented in full in a comprehensive listing including subject number, treatment, severity, seriousness, action taken, outcome, relationship to treatment, onset/stop date, and duration. The data listings for serious TEAEs and TEAEs leading to discontinuation of study treatment will be generated as well.

8.10.1.2 Adverse Event Overview

An overview of AEs will be presented by the actual treatment received overall and consisting of the number and percentage of patients experiencing at least one event for the following AE categories:

- Any TEAEs
- TEAEs related to study treatment
- Serious TEAEs
- Serious TEAEs related to study treatment
- TEAEs leading to discontinuation of study treatment
- TEAEs leading to death

Protocol CM4620-203 CONFIDENTIAL Page 27 of 31

8.10.1.3 Adverse Event by SOC and PT

The following summaries of AEs will be generated:

- Incidence of TEAEs
- Incidence of TEAEs related to study treatment
- Incidence of serious TEAEs
- Incidence of serious TEAEs related to study treatment
- Incidence of TEAEs leading to discontinuation of study treatment
- Incidence of TEAEs leading to death
- Incidence of severe TEAEs

8.10.2 Vital Signs

Vital signs will include temperature, systolic and diastolic blood pressure, respiratory rate (breaths per minute), heart rate (beats per minute) and QTc (milliseconds). Vital signs will be examined at each scheduled visit and time point. Clinically significant, treatment-emergent findings will be reported as AEs. In addition, vital signs results will be flagged as potentially clinically significant (PCS) if they meet the criteria which are defined below:

- Pulse rate >130 bpm
- Pulse rate <45 bpm
- Diastolic blood pressure >100 mmHg
- Systolic blood pressure >155 mmHg
- Systolic blood pressure <80 mmHg
- Respiration rate >25 breaths/min
- Body temperature ≥39 °C
- OTc >500 milliseconds

The number and percent of patients meeting each PCS criterion at each scheduled visit and time point will be summarized by the actual treatment and then by the overall treatment.

8.10.3 Laboratory Analyses

Local laboratory test results will be used in the summary. CBC with differential, platelets, serum chemistries, and serum procalcitonin will be summarized.

Laboratory values by visit will be summarized as boxplots. The lower and upper reference range values for lab tests will be used to grade the lab results to low, normal, and high categories. Shift tables will display:

- Shift from baseline category to the worst category
- Shift from baseline category to the last category

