8.12.7 Laboratory Analyses

At Screening, a lipase, CBC, differential, and platelets, will be performed at the local lab. For eligibility purposes, the results of the CBC collected within 24 hours of consent or following consent but prior to randomization will be used to determine the presence of SIRS (see Section 8.12.13) and a Hematocrit collected as SOC within 12 hours of consent or following consent but prior to randomization may be used for Inclusion Criterion 3c.

CBC with Differential and Platelets will be performed at 24, 48 and 72 hours, and if the patient remains hospitalized, at 120, 168, and 216 hours following SFISD as well as at Day 30 assessment. These samples will be sent to the local laboratory for analysis.

Serum Chemistries and Serum Procalcitonin will be performed at Baseline, 24, 48 and 72 hours, and if the patient remains hospitalized, at 120, 168, and 216 hours following SFISD as well as at Day 30 assessment. These samples will be sent to the local laboratory for analysis.

CBC results that should be reported in the eCRFs include absolute or percent neutrophil and lymphocyte counts. Serum chemistries reported in CRFs should include sodium, potassium, chloride, bicarbonate, blood urea nitrogen, creatinine, glucose, calcium, phosphorus, as well as magnesium, total protein, albumin, alkaline phosphatase, alanine transaminase (ALT), aspartate transaminase (AST), total bilirubin, lactate dehydrogenase (LDH), total cholesterol, triglycerides, and creatine kinase (CPK).

If a site is unable to perform any of the laboratory tests because it is not offered at the site, it will not be performed on patients randomized at the site.

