9 ADVERSE EVENTS

9.1 Definition of Adverse Event

An adverse event (AE) is defined as any untoward medical event in a patient regardless of its causal relationship to study treatment. An AE can be any unfavorable and unintended sign (including any clinically significant medical test abnormality), symptom, or disease temporally associated with the use of study drug, whether or not it is considered related to study drug administration. Included in this definition is any newly occurring event or previous condition that has increased in severity or frequency since the administration of study drug.

A medical test abnormality (e.g., laboratory test value, vital sign recording, ECG finding, physical examination finding) will be considered clinically significant and consequently recorded as an AE only if it meets one of the following criteria:

- Induces clinical signs or symptoms
- Requires active intervention
- Requires interruption or discontinuation of study medication

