9.4 Recording Adverse Events

Recording of AEs must begin after randomization. All conditions present before randomization, including untoward medical events during Screening, should be documented as medical history. Documentation shall continue until the patient dies, the patient withdraws consent, or the patient's participation in the study ends. Information to be collected includes:

- Type of event
- Date of onset
- Date of resolution
- Investigator-specified relationship to study drug and assessment of severity
- Seriousness
- Any action taken

While an AE is ongoing, changes in the severity (e.g., worsening and improving) should be noted in the source documents, but when documenting the AE, only the total duration and the greatest severity should be recorded in the case report form. AEs characterized as intermittent require documentation of onset and duration.

All AEs reported or observed during the study must be followed to resolution. Or, if not fully resolved, until the condition has stabilized, the patient dies, withdraws consent, the site is closed, or CalciMedica ends the trial, whichever is first.

AEs resulting from concurrent illnesses, reactions to concurrent medications, or progression of disease states must also be reported. Pre-existing conditions (present before the start of the AE collection period) are considered concurrent medical conditions and should NOT be recorded as AEs. However, if the patient experiences a worsening or complication of such a concurrent condition, the worsening or complication should be recorded as an AE. Investigators should ensure that the AE term recorded captures the change in condition (e.g., "worsening of...").

Each AE should be recorded to represent a single diagnosis. Accompanying signs (including abnormal laboratory test values or ECG findings) or symptoms should NOT be recorded as additional AEs. If a diagnosis is unknown, sign(s) or symptom(s) should be recorded as an AE(s).

Elective procedures (surgeries or therapies) performed to manage/treat conditions that existed prior to the patient enrolling in the trial should not be recorded as AEs but should be documented in the patient's source documents. If a planned procedure is performed early (e.g., as an emergency) because the pre-existing condition worsens, the worsening condition should be captured as an AE.

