10.8 Safety Analysis

Safety will be assessed by subject reported and Investigator observed AEs along with clinical laboratory tests (hematology and chemistries), and vital signs. Safety variables will be tabulated by treatment groups and presented for all treatment patients. Exposure to study treatments, reasons for discontinuation, deaths and causes of deaths will be tabulated. TEAEs are defined as events that first occurred or worsened after the first dose of study drug. TEAEs will be mapped to the appropriate SOC and PT according to the Medical Dictionary for Regulatory Activities (MedDRA).

Summaries will be provided for all AEs, AEs considered related to study treatment, SAEs, and related SAEs as follows:

- By maximum severity
- Incidence by SOC (by severity grade and overall)
- Incidence by PT (by severity grade and overall)

The percentage of 30 day all-cause mortality will be calculated based on each subject's date of death relative to first dose of study treatment and tabulated by treatment groups.

Laboratory test results will be used in the summary. The lower and upper reference range values for blood tests from the laboratories will be used to grade the lab results to low, normal and high. Shift tables will display (1) shift from baseline grade to the worst grade, and (2) shift from baseline grade to the last grade. Vital signs will be summarized by visit using proportion of patients with each vital sign being too high or too low according to conventionally accepted vital sign normal ranges.

Concomitant medication will be coded by the WHO Drug Dictionary and summarized by Therapeutic subgroup and PTs, using counts and percentages. Concomitant medications are the medications taken with a start date on or after the start of the administration of study treatment, or those with a start date before the start of the administration of study treatment and a stop date on or after the start of the administration of study treatment.

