8.1.4.3 Definition(s) of (Percent) Change from Baseline(s)

For numerical variables, change from baseline will be calculated as the post-baseline value minus the baseline value. If percent change from baseline is required, then percent change from baseline will be calculated as the change from baseline divided by the baseline value, multiplied by 100. If baseline value cannot be determined for a particular variable, the change from baseline and percent change from baseline will not be calculated.

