8.1.4.4 Adverse Events

Treatment-emergent AEs (TEAEs) are defined as AEs that started or worsened in severity on or after the SFISD. All adverse events will be coded from the reported term using the Medical Dictionary for Regulatory Activities (MedDRA) version 23.0 or the later version.

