8.8 Exploratory Endpoints

The development of infected pancreatic necrosis, and of sepsis will be summarized by the number of patients and treatment group.

Protocol CM4620-203 CONFIDENTIAL Page 23 of 31

Mean changes in total mGCSI-DD score from screening to discharge and to Day 30, IL-6 levels, and urine neutrophil gelatinase-associated lipocalin (NGAL) levels to each post-baseline visit will be summarized by the treatment groups.

The mean change in IL-6 levels in patients with a baseline level ≥150 pg/mL to the 72-hour visit will be summarized by the treatment group. The change in urine NGAL in patients with a baseline level ≥150 ng/mL to the 72-hour visit will be summarized by the treatment groups.

Shift tables will display the number of patients with baseline IL-6 levels >1000 pg/mL, 150-1000 pg/mL at 72 hours by the treatment groups.

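### The safety-laboratory shift tables cannot show worsening within an already abnormal category, and they leave the worst category undefined for tests that can go wrong in both directions (minor)

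*SAP*

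**What the plan says.** SAP 8.10.3 covers the blood count with differential, platelets, serum chemistries and procalcitonin. It plans boxplots of the values by visit and a three-level classification: the reference limits "will be used to grade the lab results to low, normal, and high categories". Two shift tables follow, from baseline to the worst category and from baseline to the last. Protocol 10.8 plans the same pair: "Shift tables will display (1) shift from baseline grade to the worst grade, and (2) shift from baseline grade to the last grade". Its grades are also low, normal and high, not a toxicity scale.

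Other sections bear on the point:

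- SAP 5.2 makes clinically significant change a safety endpoint for both vital signs and laboratory tests. SAP 8.10.2 sets eight numeric limits for vital signs and QTc; SAP 8.10.3 sets none for laboratory tests.
- SAP 8.1.4.3 has a general rule: "change from baseline will be calculated as the post-baseline value minus the baseline value". SAP 8.10.3 calls for no table that uses it.
- SAP 8.8 bands one biomarker numerically: "Shift tables will display the number of patients with baseline IL-6 levels >1000 pg/mL, 150-1000 pg/mL at 72 hours by the treatment groups".
- Under Protocol 9.1 an abnormal test result "will be considered clinically significant and consequently recorded as an AE only if it meets one of the following criteria": clinical signs or symptoms, a need for active intervention, or interruption or discontinuation of study drug.
- Protocol 9.4 says of pre-existing conditions that "if the patient experiences a worsening or complication of such a concurrent condition, the worsening or complication should be recorded as an AE". SAP 8.1.4.4 defines TEAEs as "AEs that started or worsened in severity on or after the SFISD".

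**The concern.** With three categories, any movement inside a category disappears. A patient above the upper limit of normal (ULN) at baseline reads high-to-high whether the value is stable or climbs steeply, and a patient below range reads low-to-low in the same way. Patients in this trial can plausibly start abnormal: white cell count is one of the four SIRS entry criteria, and an elevated hematocrit is one of the alternative entry criteria (Protocol 4.1).

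The second problem is direction. Neither document says which way is worst for a test that matters both ways. SAP 8.1.4.1 also takes the worst of tied categorical baseline values without naming a direction. Two programmers could therefore fill the same table differently and both follow the plan.

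What is at stake is the completeness of the safety report. For patients who start abnormal, there is no tabulated view, independent of the investigator's judgement, of how far each patient's values moved.

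**Working it through.** The plan states no figure for these tables, so there is nothing to reproduce. The check is of text and logic.

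**1. Which planned outputs could show a patient's worsening from that patient's own baseline?**

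| Route | Paired with own baseline? | Limit |
|---|---|---|
| Shift tables (SAP 8.10.3, Protocol 10.8) | Yes | Three categories only |
| Boxplots by visit (SAP 8.10.3) | No | Group distribution at each visit |
| Descriptive statistics by visit, where appropriate (SAP 8.1.3) | No | Group mean, spread and extremes |
| TEAE tables (Protocol 9.1 and 9.4, SAP 8.1.4.4) | In effect | Only what the investigator records under the 9.1 criteria |
| New-onset persistent organ failure (SAP 8.7.8) | In part | Excludes failure present at randomization; renal part excludes known chronic kidney disease |
| IL-6 and urine NGAL summaries (SAP 8.8) | Yes | Exploratory biomarkers, not safety laboratory tests |

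The two shift tables are the only baseline-paired tables for the safety laboratory tests.

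**2. What a three-level shift hides: creatinine as an illustration.** The modified Marshall table (Protocol Appendix 1) has five bands: <1.4, 1.4-1.8, 1.9-3.6, 3.7-4.9 and >4.9 mg/dL. The possible upward moves between bands number 5 x 4 / 2 = 10. The ULN is local and not given, so two assumed positions are shown.

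- ULN at the 1.4 boundary: four bands are high. Moves among them number 4 x 3 / 2 = 6. All 6 show as no shift, so 6 of 10 are hidden.
- ULN at the 1.9 boundary: three bands are high, giving 3 x 2 / 2 = 3 hidden moves, plus 1 within normal. So 4 of 10 are hidden, including all 3 that start high.

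These are kinds of move, not patients.

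A single case, assuming that 1.9 mg/dL exceeds the local ULN: a rise from 1.9 to 3.6 mg/dL is 3.6 / 1.9 = 1.89-fold. It stays high and stays at Marshall 2. If the failure was present at randomization, it is not new onset. It is then tabulated for that patient only if it is recorded as an adverse event, leads to renal replacement therapy, or counts under the sepsis definition, which requires infection.

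**3. When worst is undefined.** The categories that a patient shows after baseline form a non-empty subset of {low, normal, high}, and there are 7 such subsets. Two of them, {low, high} and {low, normal, high}, contain both directions and have no defined worst category. White cell count shows that this matters here: SAP 8.7.7 counts both >12,000 and <4,000 per mm³ towards SIRS.

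**4. How many chances there are.** Scheduled post-baseline draws fall at 24, 48, 72, 120, 168 and 216 hours and Day 30, so at most 7. From 72 to 216 hours they require continued hospitalization. Phase 2a median stays were 3.70 days on Auxora and 6.02 days on supportive care (Protocol 1.5.2). If these are counted from about the first infusion, they are 88.8 and 144.5 hours. That gives 3 + 1 = 4 and 4 + 1 = 5 draws for a typical patient, including Day 30.

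**The case against.** The strongest reply is that reference-range shifts to worst and last are a stated and consistent method, and that safety is purely descriptive (SAP 8.10). Boxplots and by-visit extremes show outlying values by group. A rise that causes symptoms, needs treatment or interrupts dosing becomes an adverse event. What remains uncovered is an asymptomatic, untreated worsening in a patient who was already abnormal. Earlier data raise no alarm: Phase 1 found no clinically significant laboratory abnormalities, and Phase 2a reported no untoward laboratory changes. The IL-6 table is a limited precedent, because it concerns an exploratory biomarker assayed centrally. The direction problem touches only patients who go both below and above range, and one sentence would settle it.

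Most of this stands, and it is why the point is minor. It does not close the gap. None of these routes sets a patient's extreme value against that patient's baseline by a rule that does not depend on investigator judgement. Laboratory change is a named safety endpoint, yet it gets no numeric limit where vital signs get eight.

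**Conclusion.** The point holds as a minor, inexpensive improvement. That worsening within a category goes unseen, and that worst is undefined for a patient with both low and high values, follows from the three-level design and needs no assumption. The creatinine figures rest on assumed local ULNs and only illustrate. Power, alpha and sample size are unaffected.

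Three stronger readings are tempting, and the documents do not support them.

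- A reader might infer that laboratory harm would go undetected. The boxplots, by-visit statistics and adverse event rules argue against that, and no liver, renal or CPK signal is documented.
- A reader might multiply 54 patients per arm by an assumed fraction who start high and worsen. The documents give no baseline frequencies for the chemistry tests. Such a product returns only its own assumptions, and it misses rises within the normal range, which also show as no shift.
- A reader might infer that the lipid tables are badly confounded by emulsion volume, since placebo mixes three volumes. With equal thirds, mean placebo volume is (1.25 + 0.625 + 0.3125) / 3 = 0.729 mL/kg. The single active arms then receive 1.71, 0.86 and 0.43 times that volume. However, equal active arms pooled also average 0.729, a ratio of 1.0. Phase 1 judged the cholesterol rise reversible and not clinically significant. This is a separate and weaker matter.

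**What to change.** Keep the boxplots and the shifts to the last category. In SAP 8.10.3:

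1. For tests that matter in both directions (for example white cell count, potassium, calcium and glucose), replace the single worst shift with two: baseline to lowest and baseline to highest category.
2. For ALT, AST, bilirubin, creatinine, CPK, triglycerides and cholesterol, add a table of each patient's maximum post-dose value in bands of multiples of the ULN, against the same bands at baseline. The sponsor should choose the limits per analyte. Add each patient's maximum ratio to baseline, which has no top-band ceiling.
3. For white cell count, add each patient's maximum and minimum change from baseline. Category shifts alone would still hide movement in patients who enter with an abnormal count.

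The cost is SAP wording and a few more descriptive tables. The analytes are already collected under Protocol 8.12.7, so no visit, sample or patient is added. Sites that do not offer a test will contribute nothing for it.

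Splitting placebo by volume in the lipid tables is at most an optional descriptive display. Equal thirds leave 54 / 3 = 18 placebo patients per volume, where 0 of 18 has an exact 95% upper limit of 18.5%, against 6.6% for 0 of 54. The 24 and 48 hour chemistries are drawn before the next infusion, and Phase 1 triglycerides were back to baseline within 24 hours, so peaks may be missed in any case.

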8.10.4 Arterial Blood Gas

If an arterial blood gas (ABG) has been performed as supportive care, the time of the draw and following results will be listed: the pH, PaO₂, PaCO₂, SaO₂ and FiO₂.

8.10.5 SpO_2/FiO_2

SpO₂ and FiO₂ parameters, and imputed P/F ratios will be listed.

8.11 PK Assessments

PK analysis will be performed as a separate analysis.

8.12 Subgroup Analyses

Subgroup analyses will be performed to explore how time to solid food tolerance through Day 30 visit and proof-of-concept endpoint are influenced by baseline variables and to evaluate the treatment effect at different levels of each of these variables. The Kaplan-Meier analysis, Cox model, Finkelstein-Schoenfeld Method, and Win Ratio will be performed by subgroup levels of the baseline variables listed below:

- Age ($<50 \text{ vs} \ge 50$)
- Race (White vs Asian vs Other)
- Sex (Male vs Female)
- Etiology (Alcohol vs Other)
- SIRS (Two criteria vs > Two criteria)
- Risk For Organ Failure (High vs Low as determined by values entered in eCRF)
- Hypoxemia (imputed P/F \leq 360 vs >360)
- HCT (High: HCT ≥44% for men or ≥40% for women vs Low: HCT <44% for men or <40% for women)
- Balthazar Score on Screening CECT by central reading (A or B or C, vs D or E)
- WBC (>12,000 mm³ or < 4,000 mm³ vs \leq 12,000 mm³ and \geq 4,000 mm³)
- Patients enrolled in India vs. in the United States of America

To increase the number of subjects in each comparison group of the subgroup analysis, the subgroup analysis will combine the subjects from the 1.25 mL/kg and 0.625 mL/kg groups into one pooled Auxora group. This pooled Auxora group will be compared with the placebo group. This grouping method assumes that the 1.25 mL/kg and 0.625 mL/kg groups have the similar treatment effect. If this assumption is not valid after the primary analysis of the time to solid food tolerance, the grouping method will be adjusted.

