10.2 Sample Size

A sample size of 216 patients will be randomized into four groups on a 1:1:1:1 basis, resulting in 54 patients randomized into each group. This sample size will provide 86% power for testing the difference in two populations having a median length of time of 72 and 144 hours, respectively, to tolerating solid food based on a log-rank test. This sample size will provide 80% power with a two-sided alpha of 0.05 (using the chi-squared test) to detect a 45% response rate for tolerating solid food in a Auxora dose group versus a 20% response rate in the Placebo group in the 72 hours after completion of the first study drug infusion.

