8.1.2 Significance Level and Confidence Interval

The statistical tests will be performed as two-sided with significance level of 5% unless specified otherwise. The confidence intervals will be determined with a confidence level of 95%.

Protocol CM4620-203 CONFIDENTIAL Page 11 of 31

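### SAP 8.12 analyses eleven baseline factors one level at a time and plans no estimate or test of whether the treatment effect differs between levels

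*SAP*

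**What the plan says.** SAP 8.12 gives two aims: "to explore how time to solid food tolerance through Day 30 visit and proof-of-concept endpoint are influenced by baseline variables", and to assess the treatment effect at each level of those variables. The method follows in one sentence: "The Kaplan-Meier analysis, Cox model, Finkelstein-Schoenfeld Method, and Win Ratio will be performed by subgroup levels of the baseline variables listed below". Eleven factors are listed. Ten have two levels and race has three.

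The comparison is not dose by dose. To enlarge the groups, the section will "combine the subjects from the 1.25 mL/kg and 0.625 mL/kg groups into one pooled Auxora group" and compare that group with placebo. The protocol's sample size section has patients "randomized into four groups on a 1:1:1:1 basis, resulting in 54 patients randomized into each group", so this is about 108 against 54. The grouping may be changed if the two doses do not behave alike.

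SAP 8.1.2 makes tests "two-sided with significance level of 5% unless specified otherwise", and 8.12 specifies nothing else. SAP 8.9 attaches a Finkelstein-Schoenfeld p-value to the win ratio. SAP 8.6.1 reports Cox results as hazard ratios with 95% confidence intervals. Neither document mentions an interaction term, a heterogeneity test, a multiplicity rule for subgroups, or how differences between levels are to be read.

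**The concern.** Separate fits describe each level, so they serve the second aim. They do not serve the first, because nothing in the output measures the difference between levels. The nearest substitute is to note where a p-value falls below 0.05 or an interval excludes 1, and that reflects the size of the level as much as the effect in it. An even split leaves 27 placebo patients per level, and a 25/75 split leaves about 13 in the smaller one (54 × 0.25 = 13.5).

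Three of the factors also overlap. Risk for organ failure is defined by hematocrit and hypoxemia together, and all three are analysed. A chance split in one could recur in the others and look like corroboration.

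**Working it through.** **The plan's own figures.** The documents give no figure for the subgroup analyses. Two figures in Protocol 10.2 serve as reference.

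- Binary: "80% power with a two-sided alpha of 0.05 (using the chi-squared test) to detect a 45% response rate", against 20%. This reproduces: 80.1% with 54 per arm.
- Time to event: the stated power is 86%, for "populations having a median length of time of 72 and 144 hours, respectively, to tolerating solid food based on a log-rank test". Exponential times give a hazard ratio (HR) of 144/72 = 2.0 for tolerating food. By Day 30 (720 h) the expected events are 54 × (1 − 2^−10) + 54 × (1 − 2^−5) = 106, and power = Φ(ln 2 × √(106.3/4) − 1.96) = 94.7%. A power of 86% needs about 77 events (Schoenfeld), so the stated figure is conservative and not shown to be wrong. The only use made of it here is the design HR of 2.0.

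**Inputs for the check.** 108 v 54; two-sided 0.05; the same HR in every patient; placebo median 144 h. Event totals are bounded by follow-up to Day 30 (high) and by truncating everyone at 168 h (low). The SAP censors only some patients at 168 h, so the second is a deliberate lower bound.

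- HR 2.0: 108 × 0.999 + 54 × 0.969 = 160 events (Day 30); 108 × 0.802 + 54 × 0.555 = 117 (168 h).
- HR 1.5: 160 and 106 by the same method.

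**Formulas.** For a level with d events, power p = Φ(ln HR × √(d × 1/3 × 2/3) − 1.96). For two levels, P(exactly one significant) = p1(1 − p2) + p2(1 − p1).

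**Worked example, HR 2.0, even split.**

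- Day 30: d = 80, p = Φ(2.92 − 1.96) = 83%, and 2 × 0.83 × 0.17 = 28%.
- 168 h: d = 58.5, p = Φ(2.50 − 1.96) = 71%, and 2 × 0.71 × 0.29 = 42% before rounding.

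| True HR, all patients | 50/50 split | 25/75 split |
|---|---|---|
| 1.0 | 5% (benefit only) to 10% (two-sided) | same |
| 1.25 | 20-26% | 20-27% |
| 1.5 | 41-48% | 43-53% |
| 2.0 (design) | 28-42% | 46-56% |
| 2.5 | 5-14% | 22-33% |

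**Simulation** (log-rank, 4,000 trials per setting, benefit only). HR 2.0 gave 33-46% (50/50) and 52-60% (25/75). HR 1.5 gave 38-48% and 40-52%. No effect gave about 5%.

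**Cross-check.** Assume 90% and 85% of patients have events. Half-size levels then have 48.6 and 22.95 events, and the standard error is √(1/48.6 + 1/22.95) = 0.253. HR 1.5 gives 36% power and 46% discordance; HR 2.0 gives 78% and 34%.

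**Expected count at HR 2.0.** Race with three equal levels disagrees in 67-75%. Even splits give 10 × 0.28 + 0.67 = 3.5 to 10 × 0.42 + 0.75 = 5.0 of 11. With 25/75 splits the sums are 10 × 0.46 + 0.67 = 5.3 to 10 × 0.56 + 0.75 = 6.4.

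**Interaction test, no true interaction.** At 5%, 11 × 0.05 = 0.55 factors are flagged. If the tests were independent, the chance of at least one is 1 − 0.95^11 = 43%.

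**Power for a two-fold ratio of hazard ratios, equal halves.** Φ(ln 2 / √(2/(d/2 × 2/9)) − 1.96) gives 53% with d = 157 events and 42% with d = 116.

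**The case against.** The section describes itself as exploratory, in a Phase 2 dose-ranging trial. It never says that an effect will be declared present or absent in a level by its p-value. For time to solid food tolerance it names Kaplan-Meier and Cox, not a log-rank test, and Cox output elsewhere in the SAP is a hazard ratio with a confidence interval, which is the right level-specific summary. Pooling two doses is a deliberate step to help the subgroup sizes. All of this stands, and it keeps the point minor. It does not make level-by-level results answer a between-level question, and Finkelstein-Schoenfeld p-values remain the default output for the composite in every level.

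A reader might go further in three ways that the documents do not support.

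- **That about half the factors will look discordant whatever the truth.** This needs a uniform HR near 1.5 to 1.75, or 2.0 with uneven splits. An HR of 1.5 appears nowhere in the documents, and for an even split 2p(1 − p) cannot exceed 50%, so it is close to the worst case.
- **That every level is under-powered by design.** At the design HR of 2.0 a half-size level has about 71-83% power.
- **That these subgroups will select the Phase 3 population.** Protocol 1.6 speaks only of informing Phase 3 dosing and endpoints, and SAP 8.6.1 bases dose selection on overall efficacy and safety.

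The remedy also has limits: low power, and a real chance of at least one false flag among eleven tests.

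**Conclusion.** The point holds as a low-severity improvement. SAP 8.12 asks whether the effect varies with baseline factors and plans nothing that measures the variation. With a uniform HR of 1.5 to 2.0, a significant/non-significant split is expected by chance in roughly 30-60% of two-level factors. With no effect it is about 5-10%, and with a large effect and even splits it is also small.

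The range rests on assumptions that are not in the documents: exponential times, shares between 50/50 and 25/75, unstratified analysis within levels, and 168 h and 720 h as event bounds. It also takes the pooled grouping as planned. More uneven splits can go above it. It covers time to solid food tolerance only. The composite was not calculated, because no win ratio is assumed anywhere. Overlap among factors makes discordant findings cluster but does not change the expected count.

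**What to change.** Add to SAP 8.12:

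- **Time to solid food tolerance.** For each factor, fit one Cox model with treatment, factor and treatment-by-factor term, stratified by sex and organ-failure risk as in 8.6.1. Where the factor is itself a stratification variable, its main effect is absorbed by the strata and the interaction is still estimable. Use a 2-df test for race.
- **Reporting.** Give the ratio of hazard ratios with its 95% CI and the interaction p-value, beside level-specific hazard ratios with CIs. State that subgroup differences will not be read from level-specific p-values.
- **Composite.** Compare log win ratios between levels using a bootstrap or U-statistic standard error. The SAP 8.9 form, log(win ratio) divided by Z, is unstable when a level's win ratio is near 1, because numerator and denominator both approach zero.
- **Labelling.** Call all of this exploratory and unadjusted for multiplicity, and note that hematocrit, hypoxemia and risk overlap.

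The cost is SAP wording and minor programming, plus some extra work for the bootstrap. The downside is the low interaction power and the 0.55 chance flags shown above, so a non-significant interaction must not be read as proof of a uniform effect.
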